#### **KNO3 Dose Visit 1**

- 1) Subjects will report to the Clinical Translational Research Unit (CTRU) at Washington University.
- 2) **KNO3 Gelcaps:** Subjects will receive 10 or 20 mmol of KNO3 in the form of a gelcap.
- 3) **Blood Samples:** Subjects will have blood drawn (20mL or about 1.5 tbsp). An intravenous catheter will be placed to facilitate blood sampling 5 times during the visit. The first blood sample will be obtained before ingestion of the cap and the others will be obtained once each hour for 4 hours after ingestion of the gelcap. The blood will be used to determine blood levels of nitrate and nitrite. A sample also will be obtained for measurement of blood lipids.
- 4) **Blood Pressure and Heart Rate:** Blood pressure and heart rate will be measured once before the gelcap is consumed and once each hour for 4 hours after the gelcap is consumed.

## The Inorganic Nitrate for Exercise in Heart Failure (iNIX-HF) Trial

- 5) **Breath Nitric Oxide:** Subjects will exhale into a tube attached to a portable electrochemical analyzer (NIOX VERO, Aerocrine Inc., Morrisville, NC) following the American Thoracic Society/European Respiratory Society guidelines before and 4 times after ingestion of the gelcap. Breath nitric oxide concentration provides a surrogate biomarker of whole-body NO production.
- 6) **Saliva Sample:** A sample of saliva will be obtained to determine the different types of oral bacteria residing in the mouth, based on bacterial DNA analyses. Some types of bacteria can convert nitrate to nitrite. This will be done only once.
- 7) **Exercise Test – Maximal Muscle Power:** 2 hours after ingesting the gelcap, subjects will complete the following series of tests to assess leg muscle power. A Biodex 4 isokinetic dynamometer (Biodex Medical Systems, Shirley, NY) will be used to measure maximal voluntary force and power during knee extension exercise performed with the dominant leg at angular velocities of (in order) 0, 1.57, 3.14, 4.71, and 6.28 rad/second, which equate to 0, 90, 180, 270, and 360 °/second. The chair back-chair seat angle will be set to 85° and the dynamometer adjusted to place the axis of rotation of the lever arm adjacent to the lateral femoral epicondyle. To minimize other movement, straps will be placed across the torso, hips, and thigh, and subjects will not be allowed to use the handholds. Range of motion will be determined. Next, the subject will perform 3-4 knee extensions at each velocity, with the isometric testing conducted at an angle of 1.22 rad (70°). Two minutes of rest will be allowed after each group of contractions. Strong verbal encouragement will be provided throughout all portions of the isokinetic testing.
- 8) **Exercise Test – Aerobic Capacity:** After 10 min of recovery from the muscle power testing, peak oxygen consumption ( $\dot{V}O_2$ peak) will be determined with an incremental treadmill exercise test to volitional fatigue using the modified Naughton protocol. Subjects will walk on a treadmill and breathe into a mouthpiece while wearing a nose clip (to prevent airflow through the nose). Subjects will be asked to give their maximal effort. Blood pressure and heart rhythm will be monitored. A ParvoMedics TrueOne metabolic cart will be used to measure ventilation (Ve), oxygen consumption ( $\dot{V}O_2$ ), and carbon dioxide production ( $\dot{V}CO_2$ ) throughout exercise. Data from this test will be used to quantify Ve/ $\dot{V}O_2$ , Ve/ $\dot{V}CO_2$ , ventilatory threshold (defined using the V-slope method), oxygen uptake efficiency slope (OUES), and  $\dot{V}O_2$ peak. Subjects will also be asked to give a rating of perceived exertion (RPE) on the Borg scale (6-20) and their perceived dyspnea on a five-point visual-analog scale.

### $KNO_3$ Dose Visit 2

At least 7 days after  $KNO_3$  Dose Visit 1, subjects will receive a different gelcap than they received during Dose Visit 1 (i.e., 10 or 20 mmol  $KNO_3$ ) and then complete all of the assessments listed under  $KNO_3$  Dose Visit 1 except the saliva sample.

### **Aim 1 Sub-Study: Pharmacokinetics**

To determine the time course of effects of a single 10 mmol dose of  $KNO_3$  on plasma nitrate and nitrite concentrations, breath nitric oxide (NO) concentration, blood pressure, and heart rate at rest. Blood samples will be drawn and breath NO will be sampled before

## The Inorganic Nitrate for Exercise in Heart Failure (iNIX-HF) Trial

dosing, every hour for 3 hours after  $\text{KNO}_3$  ingestion, and at 4.5, 6, 12, 18 (optional), and 24 hours post-dose.

### Screening Visit

- 1) **Consent:** All study procedures will be reviewed with the participant before he/she provides written informed consent. Consent includes giving permission for the investigators to review their medical records.
- 2) **Blood Sample:** A blood sample will be drawn for basic screening laboratories, including glucose,  $\text{K}^+$ , and creatinine (for estimation of glomerular filtration rate).
- 3) **Physical Exam:** Subjects will have a brief history and physical examination. These will not be done with participants who have had a physical exam within the past 6 months.
- 4) **Resting Echocardiogram:** A resting echocardiogram will be performed to enable assessment of cardiac blood flow. An intravenous contrast agent may be used to obtain a clearer assessment of cardiac blood flow, if needed. The echocardiogram may not be necessary if the participant had an echocardiogram within the past 12 months.
- 5) **Questionnaire:** Subjects will be asked to complete a Health Questionnaire.
- 6) **Instructions to participants:** Subjects will be instructed to refrain from using mouthwash, antacids, proton pump inhibitors, or chewing gum before the  $\text{KNO}_3$  dose visit.

### Dose Visit

- 1) Subjects will report to the Clinical Translational Research Unit (CTRU) at Washington University for either two outpatient visits or a single inpatient (overnight) visit, based on their preferences.
- 2)  **$\text{KNO}_3$  Gelcaps:** Subjects will receive a single  $\text{KNO}_3$  gelcap containing 10 mmol of inorganic nitrate.
- 3) **Blood Samples:** An intravenous catheter will be placed to facilitate blood sampling throughout the visit. The total amount of blood drawn will be ~30 mL (2.0 Tbsp). The first blood sample will be obtained before ingestion of the  $\text{KNO}_3$  gelcap and the others will be obtained once each hour for 3 hours after ingestion of the gelcap and at 4.5, 6, 12, 18 (optional), and 24 hours post-dose. If this sub-study is completed as two outpatient visits, then the 18h blood sample is optional and the 24h blood sample will be drawn at the second visit. For inpatient visits, all blood samples will be drawn during this dose visit.
- 4) **Breath Nitric Oxide:** Subjects will exhale into a tube attached to a portable electrochemical analyzer (NIOX VERO, Aerocrine Inc., Morrisville, NC) following the American Thoracic Society/European Respiratory Society guidelines before and several times after ingestion of the gelcap, on the same schedule as the post-dose blood samples. Breath nitric oxide concentration provides a surrogate biomarker of whole-body NO production.
- 5) **Blood Pressure and Heart Rate:** Blood pressure and heart rate will be measured once before the gelcap is consumed and several times after ingestion of the gelcap, on the

## The Inorganic Nitrate for Exercise in Heart Failure (iNIX-HF) Trial

same schedule as the post-dose blood samples.

### **Visit 2 (only needed if the dose visit was an outpatient visit)**

- 1) Subjects will report to the Clinical Translational Research Unit (CTRU) at Washington University approximately 23.5 hours after they received the KNO3 gelcap.
- 2) **24h Assessments:** The 24h blood sample will be drawn, breath nitric oxide will be assessed, and blood pressure and heart rate will be measured.

### **Aim 2. Randomized Controlled Trial of Potassium Nitrate (KNO3) Therapy for 2 Weeks**

The effects of KNO3 therapy on  $\dot{V}O_2$ peak and maximal muscle power in patients with HFrEF will be evaluated in a randomized, placebo-controlled trial. The KNO3 dose used in this aim will be 10 mmol daily. The treatment (or placebo) period will be 2 weeks, with measurements of  $\dot{V}O_2$ peak and maximal muscle power completed before and at the end of the intervention using the same methodology as in Aim 1.

#### **Screening Visit.**

The screening visit procedures will be the same as for Aim 1 above. If a subject participated in Aim 1, then he/she will not have to repeat the screening procedures for Aim 2.

#### **Exercise Testing Visit 1.**

- 1) Subjects will report to the Clinical Translational Research Unit (CTRU) at Washington University.
- 2) **Blood Samples:** Subjects will have blood drawn (20mL or about 1.5 tbsp) to determine blood levels of nitrate and nitrite using HPLC. A sample also will be obtained for measurement of potassium and blood lipids.
- 3) **Blood Pressure and Heart Rate:** Blood pressure and heart rate will be measured once before the gelcap is consumed and once each hour for 4 hours after the gelcap is consumed.
- 4) **Breath Nitric Oxide:** Subjects will exhale into a tube attached to a portable electrochemical analyzer (NIOX VERO, Aerocrine Inc., Morrisville, NC) following the American Thoracic Society/European Respiratory Society guidelines.
- 5) **Saliva Sample:** A sample of saliva will be obtained to determine the different types of oral bacteria residing in the mouth, based on bacterial DNA analyses. Some types of bacteria can convert nitrate to nitrite. This will not be done if the subject participated in Aim 1.
- 6) **Exercise Test – Maximal Muscle Power:** Subjects will complete the following series of tests to assess leg muscle power. A Biodek 4 isokinetic dynamometer (Biodek Medical Systems, Shirley, NY) will be used to measure maximal voluntary force and power during knee extension exercise performed with the dominant leg at angular velocities of (in order) 0, 1.57, 3.14, 4.71, and 6.28 rad/second, which equate to 0, 90, 180, 270, and 360 °/second. The chair back-chair seat angle will be set to 85° and the dynamometer adjusted to place the axis of rotation of the lever arm adjacent to the lateral femoral

## The Inorganic Nitrate for Exercise in Heart Failure (iNIX-HF) Trial

epicondyle. To minimize other movement, straps will be placed across the torso, hips, and thigh, and subjects will not be allowed to use the handholds. Range of motion will be determined. Next, the subject will perform 3-4 knee extensions at each velocity, with the isometric testing conducted at an angle of 1.22 rad (70°). Two minutes of rest will be allowed after each group of contractions. Strong verbal encouragement will be provided throughout all portions of the isokinetic testing.

- 7) **Exercise Test – Aerobic Capacity:** After 10 min of recovery from the muscle power testing, peak oxygen consumption ( $\dot{V}O_2$ peak) will be determined with an incremental treadmill exercise test to volitional fatigue using the modified Naughton protocol. Subjects will walk on a treadmill and breathe into a mouthpiece while wearing a nose clip (to prevent airflow through the nose). Subjects will be asked to give their maximal effort. Blood pressure and heart rhythm will be monitored. A ParvoMedics TrueOne metabolic cart will be used to measure ventilation (Ve), oxygen consumption ( $\dot{V}O_2$ ), and carbon dioxide production ( $\dot{V}CO_2$ ) throughout exercise. Data from this test will be used to quantify Ve/ $\dot{V}O_2$ , Ve/ $\dot{V}CO_2$ , ventilatory threshold (defined using the V-slope method), oxygen uptake efficiency slope (OUES), and  $\dot{V}O_2$ peak. Subjects will also be asked to give a rating of perceived exertion (RPE) on the Borg scale (6-20) and their perceived dyspnea on a five-point visual-analog scale.
- 8) **KNO3 Gelcaps:** Subjects will receive a 2-week supply of KNO3 gelcaps or placebo gelcaps in a double-blinded manner (i.e., neither the subject nor the investigators will know which gelcap the subject receives).

### **Exercise Testing Visit 2.**

Two weeks after Exercise Testing Visit 1, subjects will report to the Clinical Research Unit (CRU) at Washington University after an overnight fast and repeat all of the procedures that were performed during Exercise Testing Visit 1 (except the saliva sample).

### **Safety Monitoring:**

We will make every effort to minimize risks by observing and monitoring participants during testing and throughout the 2-week and 6-week treatment periods. Emergency equipment and trained personnel are available to deal with an emergency that may arise during assessments in the clinical research unit. The risk of bruising or infection at an IV site will be minimized by having experienced personnel trained in the appropriate sterile techniques place the IVs. Possible risks associated with the echocardiogram procedures include an allergic reaction to the contrast agent, an allergic skin reaction to the electrode gel, and mild discomfort due to the light pressure of the ultrasound probe. The risk of an allergic reaction to the contrast agent will be minimized by not using contrast in anyone with a known allergy, not using contrast unless necessary for adequate image analysis, and monitoring subjects closely after the contrast agent is administered.

If any particular question on a questionnaire makes the subject uncomfortable, he/she may discuss its importance and the need to answer it with the research team member. They may

## The Inorganic Nitrate for Exercise in Heart Failure (iNIX-HF) Trial

choose not to answer any question. If a subject has an incidental finding on his/her echocardiogram, blood work, or physical exam that is noted and is clinically important, he/she will be made aware of it through an incidental finding letter. He/she will be advised to share the information with his/her physician.

The data will be reviewed by the PI at least every 6 months. [name] will also review the relevant data (events, complaints, and the results of all the study endpoints) at least once each year. The safety monitoring panel is comprised of [name]; [name]; and [name].

### **Data Analysis:**

**Aim 1:** Data comparing the 2 doses of KNO3 on exercise performance, plasma NO3, plasma NO2, and breath NO will be analyzed using two-way (i.e., treatment x time) analysis of variance (ANOVA) for repeated measures using an alpha set at 0.05. In addition, the changes in measured variables will be analyzed using univariable regression methods.

**Aim 1 Sub-Study:** Pharmacokinetics data from the blood samples will be used to determine the time course and peak plasma concentrations of nitrate and nitrite in response to a single dose (10 mmol) of KNO3.

**Aim 2:** Data from the randomized, controlled trial of 2 weeks of KNO3 treatment will be analyzed using analyses of covariance in which the post-treatment value of the outcome measure will be the dependent variable and the pre-treatment value and the study group will be the independent variables. Additional analyses will adjust for sex as a covariate. The mean and standard deviation of the pre- to post-treatment change in the two outcome measures (i.e.,  $\dot{V}O_2$ peak and maximal muscle power) will serve as a guide for power calculations in the subsequent RCT for which this application is a prelude. In all analyses of covariance, regression residuals will be evaluated so we can assess the fit of the model. If the model fit is poor, we will explore data transformations that improve the fit and, if such transformations cannot be found, it is possible that we will analyze the data using semi parametric methods based on the ranks of the data. Since experience suggests that both outcome measures tend to be normally distributed, it is unlikely that these alternative approaches will prove necessary.

### **Sample Size Estimation:**

**Aim 1:** Sample sizes were estimated using data from our previous beetroot juice (BRJ) study, in which the BRJ beverage contained 11.2 mmol of nitrate. Based on average breath NO measured 1 hour, 2 hours, and 3 hours after consuming the BRJ, breath NO increased 12 +/- 11 ppb in response to 11.2 mmol nitrate, for an effect size of 1.1. If we assume a comparable increase with a KNO3 capsule relative to placebo, then approximately 6 subjects would be sufficient to provide a power of more than 0.9 at alpha=0.05. However, a larger sample size will be needed to determine the effects of different doses of the KNO3 capsule on exercise performance, plasma NO3, and plasma NO2, as these have not been studied previously. To be conservative

## **The Inorganic Nitrate for Exercise in Heart Failure (iNIX-HF) Trial**

and based on what we know about variability in exercise tolerance among HF patients, we will enroll 25 subjects, with the goal of obtaining complete data on 20 subjects. Power calculations were performed using G\*Power 3.1.9.2.

**Aim 1 Sub-Study:** The sample size will be approximately 10 participants.

**Aim 2:** While this aim is not designed to reach statistical significance with adequate power, we have performed power computations to estimate the magnitude of the improvement in the two outcomes (i.e.,  $\dot{V}O_2$ peak and maximal muscle power) that could be detected with 10 subjects in each group. Those computations are based on two-sided tests at the 0.05 level of significance. Our preliminary aerobic capacity data indicate that HFrEF patients will have a baseline  $\dot{V}O_2$ peak value of  $22.5 \pm 5.5$  mL/kg/min. Given these data, the power to detect an increase in  $\dot{V}O_2$ peak of 32.4% will be 0.8; the power to detect an increase in  $\dot{V}O_2$ peak of 37.8% will be 0.9. Our preliminary muscle power data suggest that HFrEF patients will have a mean baseline maximal knee extensor power of  $4.2 \pm 1.1$  W/kg. Using these data and 10 subjects per group, the power will be 0.8 if the magnitude of the increase in knee extensor power is 35.7%; the power will be 0.9 if the increase in knee extensor power is 40.5%.

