### **Study Aims:**

**Aim 1:** To determine the optimum dose of inorganic nitrate to improve exercise performance (i.e., aerobic capacity and muscle power) in patients with heart failure and reduced ejection fraction (HFrEF). Aerobic capacity will be assessed by peak oxygen consumption ( $\dot{\text{V}}\text{O}_{2\text{peak}}$ ) and muscle power will be assessed as maximal knee extensor power using a Biomedex machine. This is a double-blind, cross-over study aim in which each participant will receive single doses of potassium nitrate (10 or 20 mmol  $\text{KNO}_3$ ) administered in gelatin capsules in random order one week apart.

**Aim 1 Sub-Study: Pharmacokinetics.** To determine the time course of effects of a single 10 mmol dose of  $\text{KNO}_3$  on plasma nitrate and nitrite concentrations, breath nitric oxide concentration, blood pressure, and heart rate at rest. Blood samples will be drawn before dosing, every hour for 3 hours after  $\text{KNO}_3$  ingestion, and at 4.5, 6, 12, 18 (optional), and 24 hours post-dose. Plasma levels of nitrate and nitrite will be quantified using HPLC.

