## The Inorganic Nitrate for Exercise in Heart Failure (iNIX-HF) Trial

**Aim 2:** To determine the effects of 2 weeks of inorganic nitrate therapy vs. placebo on aerobic capacity and muscle power in patients with HFrEF. The dose for this aim will be 10 mmol of  $\text{KNO}_3$  daily in a single gelatin capsule taken in the morning. This dosing regimen is based on the results of Aim 1, which revealed that the beneficial effects on exercise performance were not statistically different for the 10 and 20 mmol doses taken on one occasion in the morning, whereas tolerability was lower with the 20 mmol dose. The rationale for taking the 10 mmol dose once daily is based on the half-life of  $\text{KNO}_3$ .

**Aim 3:** To determine the effects of 6 weeks of inorganic nitrate therapy vs. placebo on aerobic capacity and muscle power in patients with HFrEF. The dose for this aim will be 10 mmol of  $\text{KNO}_3$  daily in a single gelatin capsule taken in the morning. This dosing regimen is based on the results of Aim 1, which revealed that the beneficial effects on exercise performance were not statistically different for the 10 and 20 mmol doses taken on one occasion in the morning, whereas tolerability was lower with the 20 mmol dose. The rationale for taking the 10 mmol dose once daily is based on the half-life of  $\text{KNO}_3$ .

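### Aim 1's repeated-measures ANOVA, in its usual form, drops anyone who misses a dose visit, and the plan has no rule for the up to 5 of 25 participants it allows to be incomplete

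*Combined protocol and SAP*

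**What the plan says.** Aim 1 is a two-dose cross-over, with single doses "administered in gelatin capsules in random order one week apart" (Study Aims, Aim 1). At the second visit, at least 7 days later, "subjects will receive a different gelcap than they received during Dose Visit 1" (KNO3 Dose Visit 2).

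The enrolment target is in Sample Size Estimation, Aim 1: "we will enroll 25 subjects, with the goal of obtaining complete data on 20 subjects".

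Data Analysis, Aim 1 says that exercise performance, plasma nitrate, plasma nitrite and breath NO "will be analyzed using two-way (i.e., treatment x time) analysis of variance (ANOVA) for repeated measures using an alpha set at 0.05". It adds that "the changes in measured variables will be analyzed using univariable regression methods". It gives no analysis population, missing-data method or replacement rule, and neither does any other section for Aim 1.

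Under KNO3 Dose Visit 1, each visit has its own pre-dose and four hourly post-dose blood samples, and breath NO is measured before and four times after the gelcap. The exercise tests are done only after dosing.

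Study Aims, Aims 2 and 3, report Aim 1 as already informative. Effects on exercise performance did not differ statistically between doses, "whereas tolerability was lower with the 20 mmol dose", and the dose for both later aims rests on these two findings.

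**The concern.** The within-person dose contrast exists only for people with both visits. A conventional repeated-measures ANOVA works on complete rows, so a participant who attends once contributes nothing, not even to the dose that was received. For nitrate, nitrite and breath NO this discards a valid pre-to-post response that has already been collected.

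If failure to return were related to what happened at the first visit, the analysed set would be those who managed both doses and not those randomised. The statement on tolerability makes that possibility credible. At stake are the validity and precision of the reported 10 versus 20 mmol contrast.

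**Working it through.** **1. The plan's own figure.** 25 enrolled and 20 complete leave 25 - 20 = 5, and 5/25 = 20%. In the other direction, 20/(1 - 0.20) = 25. The arithmetic is consistent, but the 20% is implied by the enrolment allowance and not stated as a rate.

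**2. Inputs for a stress case.**
- Breath NO response: SD 11 ppb, from the beetroot juice data in Sample Size Estimation, Aim 1. Applying it to each dose visit is an assumption.
- VO2peak: SD 5.5 mL/kg/min, the baseline value in Sample Size Estimation, Aim 2.
- Between-visit correlation r: not in the documents. Assumed 0, 0.3 and 0.5 for breath NO, and 0.5, 0.7, 0.8 and 0.9 for VO2peak.
- Sequences: 12 participants given 10 mmol first and 13 given 20 mmol first.
- True dose difference: 0.
- Loss: among the 13 given 20 mmol first, the 5 with the lowest first-visit values do not return. This is deliberately extreme.

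**3. Bias of the completer estimate.** The estimate is the average of the two sequence-specific mean paired differences (20 minus 10). The 8 highest of 13 standard normal values average 0.584. The retained participants' first-visit (20 mmol) mean is therefore raised by 0.584 x SD and their second-visit mean by r x 0.584 x SD. Only one of the two sequences is affected, so

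bias = 0.5 x 0.584 x SD x (1 - r) = 0.292 x SD x (1 - r).

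| Outcome | r | Formula | Simulated bias / SE | Ratio |
|---|---|---|---|---|
| Breath NO, ppb | 0 | 0.292 x 11 x 1.0 = 3.21 | 3.16 / 3.44 | 0.92 |
| | 0.3 | 0.292 x 11 x 0.7 = 2.25 | 2.22 / 2.83 | 0.78 |
| | 0.5 | 0.292 x 11 x 0.5 = 1.61 | 1.64 / 2.48 | 0.66 |
| VO2peak, mL/kg/min | 0.5 | 0.292 x 5.5 x 0.5 = 0.80 | 0.83 / 1.24 | 0.67 |
| | 0.7 | 0.292 x 5.5 x 0.3 = 0.48 | 0.48 / 0.98 | 0.49 |
| | 0.8 | 0.292 x 5.5 x 0.2 = 0.32 | 0.34 / 0.78 | 0.44 |
| | 0.9 | 0.292 x 5.5 x 0.1 = 0.16 | 0.16 / 0.57 | 0.28 |

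The simulation used 4,000 replicates per setting. Repeat runs gave about 1.5 to 3.3 ppb and 0.2 to 0.8 mL/kg/min. An all-data estimate (generalised least squares with known covariance, standing in for a mixed model) had bias near 0 in every setting.

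**4. Random loss of 5.** There is no bias. Reduction in standard error from using all data, 1 - (all-data SE / completer SE):
- Breath NO: 1 - 3.31/3.54 = 6.5%; 1 - 2.77/2.92 = 5.1%; 1 - 2.38/2.46 = 3.3%.
- VO2peak: 1 - 1.19/1.23 = 3.3%; 1 - 0.95/0.97 = 2.1%; 1 - 0.77/0.78 = 1.3%; 1 - 0.55/0.55 = 0%.

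**5. Which model.** Losing 5 from one sequence leaves 12 and 8 completers, so dose and period are no longer balanced. With an assumed period effect of 1 mL/kg/min, a mixed model with dose but no period term is biased by about 0.14 to 0.18 mL/kg/min for VO2peak. At r = 0.9 that is as large as the completer bias of 0.16. Adding period removes it.

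**The case against.** Much of the opposing case stands.

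- *The allowance is not a forecast.* A reader might infer that the trial expects 20% to miss a dose visit. The text gives only a goal and an enrolment number. Some of the five could fail screening before any dose, or attend both visits with single measures missing. Anyone never dosed adds nothing to a mixed model either.
- *Dose-related loss is not documented.* A reader might infer that poor tolerability at 20 mmol kept people from returning. The protocol says only that tolerability was lower. It does not say that anyone missed a visit, and it gives no completer numbers.
- *The dose choice is not undermined.* A reader might infer that the 10 mmol choice rests on a biased comparison. The modelled bias favours 20 mmol, whereas 10 mmol was chosen, so removing it would not count against that choice.
- *The stress case is extreme.* All losses come from one sequence and are exactly the lowest values. Nothing in the documents links low breath NO to failure to return. Even so, the bias stays below one standard error. Maximal muscle power was not simulated.
- *The supplementary regression might use single visits.* It could use one visit's biomarker change, but its model and handling of missing visits are not described, so it does not clearly retain these participants in the dose contrast. Nor is listwise deletion stated; it is the conventional behaviour of the named method.
- *Aim 1 is already reported.* Any change is now a re-analysis.

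What remains is that the plan allows for incomplete participants, names a method that conventionally drops them, and provides no alternative.

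**Conclusion.** The point holds as a gap in the Aim 1 analysis, with modest consequences. Up to 5 of 25 (20%) may lack complete data, and under the conventional repeated-measures ANOVA those who miss a dose visit leave the dose contrast, including any complete biomarker series they supplied.

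Under the constructed extreme the completer bias is about 1.5 to 3.3 ppb for breath NO and 0.2 to 0.8 mL/kg/min for VO2peak, at most about 0.9 of a standard error. Under random loss only precision is affected, by about 0 to 6%. These sizes rest on the borrowed SDs, the assumed correlations and the assumed loss pattern, whose direction is set by construction.

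The documents do not show that informative loss occurred or that the dose choice was wrong. A better method is available at the cost of analysis work alone, so the change is worth making.

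**What to change.** In Data Analysis, Aim 1:

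- Define complete data and the analysis population as everyone with at least one dose visit.
- Replace the repeated-measures ANOVA with a linear mixed model with fixed dose and period and a random participant effect. For the serial biomarkers add time and dose x time, and adjust for that visit's own pre-dose value.
- Keep the completer analysis as a sensitivity analysis.
- Report non-completion of each visit by dose received and by sequence, next to the dose contrast.

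Because the protocol already reports Aim 1 results, apply this to the final analysis or report and label it as a re-analysis.

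The cost is revised text and some analysis time, with no new participants, visits or measurements. There are two downsides. The model relies on data being missing at random, so neither it nor the completer analysis fully corrects loss that depends on a value never observed, such as a visit abandoned part-way. For exercise outcomes the gain is small when between-visit correlation is high.

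### Do the Aim 2 detectable effects need recalculating because they take no account of the planned baseline adjustment?

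*Combined protocol and SAP*

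**What the plan says.** Under Sample Size Estimation, Aim 2, the protocol says that "this aim is not designed to reach statistical significance with adequate power" and then reports what 10 participants per group could detect. On method it says only this: "Those computations are based on two-sided tests at the 0.05 level of significance". The inputs are a baseline VO2peak of 22.5 ± 5.5 mL/kg/min and a baseline knee extensor power of 4.2 ± 1.1 W/kg. The outputs are 32.4% ("peak of 32.4% will be 0.8") and 37.8% for VO2peak, and 35.7% ("the power will be 0.8 if the magnitude of the increase in knee extensor power is 35.7" per cent) and 40.5% for knee power, at 80% and 90% power respectively.

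Under Data Analysis, Aim 2, the planned model is ANCOVA: "post-treatment value of the outcome measure will be the dependent variable and the pre-treatment value and the study group will be the independent variables". The same paragraph names a product of this aim that will guide the power calculation for a later trial: "The mean and standard deviation of the pre- to post-treatment change in the two outcome measures".

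**The concern.** A power statement should describe the analysis that will be run. ANCOVA removes the part of the outcome variance that the baseline value explains, so its error SD is SD × √(1 − r²), where r is the pre-post correlation. The Aim 2 calculation shows only the between-subject baseline SD. It gives no r, no residual SD and no SD of change, and it does not say that the baseline adjustment was left out. If r is high, as it can be for repeated exercise tests, the planned analysis could detect a much smaller effect than the paragraph reports. Since the paragraph exists to report that quantity, a reader could come away with too pessimistic a view of Aim 2, or carry the unadjusted SD into the design of the next trial.

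**Working it through.** **Inputs from the documents.** n = 10 per group; two-sided alpha 0.05; SD 5.5 with mean 22.5; SD 1.1 with mean 4.2. The value of r is not in the documents and is varied below.

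**Step 1: reproduce the stated figures.** For a two-sample t test with 18 df, power comes from the noncentral t with noncentrality d × √(10/2), where d is the difference divided by the SD. Solving gives d = 1.3249 for 80% power and d = 1.5337 for 90%.

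| Outcome, power | d × SD | Rounded up | Divided by baseline mean | Stated | t-test power at rounded difference |
|---|---|---|---|---|---|
| VO2peak, 0.8 | 1.3249 × 5.5 = 7.287 | 7.3 | 7.3/22.5 = 32.4% | 32.4% | 0.801 |
| VO2peak, 0.9 | 1.5337 × 5.5 = 8.435 | 8.5 | 8.5/22.5 = 37.8% | 37.8% | 0.904 |
| Knee power, 0.8 | 1.3249 × 1.1 = 1.457 | 1.5 | 1.5/4.2 = 35.7% | 35.7% | 0.822 |
| Knee power, 0.9 | 1.5337 × 1.1 = 1.687 | 1.7 | 1.7/4.2 = 40.5% | 40.5% | 0.904 |

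All four figures agree, provided the differences were always rounded up. Without rounding they would be 32.4%, 37.5%, 34.7% and 40.2%. The normal approximation gives power of 0.84 to 0.93 at the stated effects, a one-sided t test 0.89 to 0.95, and a paired t test with 10 subjects 0.96 to 0.99, so none of these fits.

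**Step 2: is the t test the only reading?** No. A t test on change scores has SD × √(2(1 − r)), which equals the baseline SD at r = 0.5, so it gives identical results there. ANCOVA at a low r is also close, as Step 3 shows.

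**Step 3: the planned ANCOVA over assumed r.** Residual df = 20 − 3 = 17. The standard error is SD × √((1 − r²) × (17/16) × 2/10), where 17/16 is the average variance penalty for chance baseline imbalance. At r = 0 the detectable standardised difference is 1.370 (80%) or 1.586 (90%); each is then multiplied by √(1 − r²), by the SD, and divided by the mean. For example, VO2peak at 80% power and r = 0.5: 1.370 × 0.866 × 5.5/22.5 = 29.0%.

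| Assumed r | VO2peak 0.8 | VO2peak 0.9 | Knee 0.8 | Knee 0.9 |
|---|---|---|---|---|
| 0 | 33.5% | 38.8% | 35.9% | 41.5% |
| 0.25 | 32.4% | 37.5% | 34.8% | 40.2% |
| 0.5 | 29.0% | 33.6% | 31.1% | 36.0% |
| 0.7 | 23.9% | 27.7% | 25.6% | 29.7% |
| 0.8 | 20.1% | 23.3% | 21.5% | 24.9% |
| 0.9 | 14.6% | 16.9% | 15.6% | 18.1% |
| Stated | 32.4% | 37.8% | 35.7% | 40.5% |

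ANCOVA reaches the stated power at r of about 0.25 (VO2peak, 0.8), 0.10 (knee power, 0.8) and 0.22 (both 0.9 figures). Simulation of the fitted ANCOVA (40,000 trials per r) at a 32.4% VO2peak difference gave power of 0.777, 0.802, 0.877, 0.965 and 0.994 for r = 0, 0.25, 0.5, 0.7 and 0.8, in line with the formula.

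**Step 4: what the range assumes.** It takes the post-treatment SD to equal the baseline SD, and all 20 participants to complete. With 9 completers per group, ANCOVA power at 32.4% is 0.75 at r = 0.25; with 8 it is 0.78 even at r = 0.5. No dropout allowance is stated for Aim 2.

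**The case for a change.** The best case for a change is that the paragraph has one job, to say what 10 per group can detect, and on any reading it does not tell the reader which test the answer belongs to. If r were 0.7, the planned analysis could detect about 24% in VO2peak, not 32%. Naming the test and tabulating the ANCOVA effects over r would take one paragraph, and it might keep an unadjusted baseline SD out of the next trial's calculation.

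Part of this stands. The figures show no credit for the covariate, and a sentence saying so would be clearer. The rest does not carry the point to a change:

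- The paragraph prints its mean, SD, group size, alpha and sidedness, so a statistician can see that no correlation was used.
- No r can be taken from the documents. Aim 1's two visits would be an imperfect proxy: muscle power is tested after dosing ("2 hours after ingesting the gelcap, subjects will complete the following series of tests to assess leg muscle power"), and at the second visit "subjects will receive a different gelcap than they received during Dose Visit 1".
- Labelling the figures as conservative would introduce a claim the documents cannot support. It depends on r, on the SD staying the same and on full completion, and no single threshold of r fits all four figures.
- The later trial is to be guided by the change-score mean and SD that Aim 2 itself will supply, not by the baseline SD used here.

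**Conclusion.** No change is needed. The stated figures are arithmetically sound for a two-sample t test on the baseline SD, allowing for upward rounding, and nothing in the documents shows them to be wrong for the planned analysis. The gap between them and ANCOVA cannot be sized without r. For VO2peak at 80% power it runs from about 1 percentage point in the optimistic direction at r = 0 (33.5% against 32.4%) to about 18 points in the conservative direction at r = 0.9 (14.6% against 32.4%), given an unchanged SD and 20 completers.

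Nothing hangs on where in that range the truth lies. The protocol declines to claim adequate power for Aim 2, presents 10 per group as given rather than derived from these effects, and fixes the ANCOVA separately. Using the baseline SD before any change data exist is a fair simplification for a pilot. Naming the test would be a courtesy to the reader; it would not alter the sample size, the conduct, the analysis or any conclusion drawn from it.
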